Hypertension is major health problem for postmenopausal women. Hypertension is more likely to be uncontrolled in women, despite medication use. Medications to block the angiotensin II pathway are commonly used to treat hypertension. However, recent data in animals suggest that multiple pathways are involved in blood pressure control in females. Specifically, blocking the angiotensin II pathway along with the endothelin-1 pathway resulted in a larger drop in blood pressure in these animals compared to single drug therapy. These blood pressure lowering effects observed in the female animals may be related to the interactions between angiotensin II and endothelin-1. Both angiotensin II and endothelin-1 are potent vasoconstrictors that can cause an increase in blood pressure, and these substances interact to cause additive effects on constricting blood vessels. The aims of this study are to examine how angiotensin II and endothelin-1 interact to regulate blood vessel function in hypertensive postmenopausal women. To do this, we will recruit women with elevated blood pressure not taking blood pressure medications, and test their blood vessel function on 2 separate visits: 1) baseline, and 2) after 14-days of losartan (an angiotensin II receptor blocker). Blood vessel function will be assessed using a technique called microdialysis, which involves placing tiny sterile plastic tubes (microdialysis probes) in the surface layer of the skin on the forearm, and blood flow will be measured using a small disk with a laser. We will also recruit normotensive women to complete 2 visits to assess blood vessel function pre/post 14 days as a control (no losartan administration).

6. PROCEDURES Describe all procedures involving human subjects for this protocol. Include copies of all surveys and research measures.

We will recruit postmenopausal women with high BP (≥ 130 and/or 80 mmHg) and normotensive postmenopausal women (ages 50-70 years). Women with high BP will complete 5 visits (screening/orientation, VO₂max test, Blood Vessel Assessment 1, Blood draw to check electrolytes and kidney function, and Blood Vessel Assessment 2), and normotensive women will complete 4 visits (screening/orientation, VO₂max test, Blood Vessel Assessment 1, and Blood Vessel Assessment 2).

Procedures in Women with high BP (5 visits):

Visit 1: Screening/orientation: The first visit is about 1 hour long and includes

- 1). Completion of informed consent, medical history, and menstrual cycle history
- 2). Measures of height and weight,
- 3). Measures of resting blood pressure and 12-lead electrocardiogram
- 4). Blood Draw

Participants will be fasted from food, caffeine, and alcohol (12 hours) and exercise (24 hours). Informed consent will be obtained by [name], study PI, [name], Lab/Study Coordinator, or doctoral student trained by [name]. Subjects will also be familiarized with the laboratory and experimental procedures. The blood draw and electrocardiogram will be done by a trained healthcare professional at the Nurse Managed Primary Care Center (NMPCC). Blood will be analyzed for cholesterol, electrolytes, kidney and liver function, c-reactive protein, and blood glucose (sugar). All screening results will be reviewed by a Nurse Practitioner at the NMPCC. In the event that the test results are abnormal, the NMPCC will refer the subject to their physician for follow-up and they will not be able to participate in the research study. Participants will be provided a HIPAA authorization form that includes permission for sharing of patient protected health information with the research team. Women will also be given a 24 hour ambulatory blood pressure monitor, and instruction on how to wear and operate the monitor. They will don the monitor at the completion of Visit 1. The blood pressure monitor measures BP every 20 minutes during the day, and every 30 minutes at night. Women will return the monitor the next day. When they return the monitor, we will ask that they be seated for 5-10 minutes, and we will take 3 resting blood pressure measures using an automated brachial blood pressure cuff. At the end of this visit we will give participants a standard blood pressure monitor to take home (Omron). This device is often used for adults to monitor blood pressure at home. The device takes 3 blood pressures and reports the average of these readings on the device. Women will be instructed to take seated resting blood pressures at home 3 times each week for 2 weeks. Blood pressures should be taken in the morning, at lunchtime, and again in the evening. Instructions will be provided along with a log to record the readings and time of day. Participants will return the BP monitor and log when they return to the lab prior to Visit 2.

Two to three days prior to Visit 2, women will be given a 24 hour ambulatory blood pressure monitor, and instruction on how to wear and operate the monitor. They will don the monitor the day before Visit 2. The blood pressure monitor measures BP every 20 minutes during the day, and every 30 minutes at night. Women will return the monitor the third visit.

Visit 2: Blood Vessel Assessment 1: The second visit lasts approximately 5 hours. Measurements will be conducted in the Cardiovascular Core Lab at STAR Health Sciences Complex. Subjects will be asked not to drink alcohol and caffeine for 12 hours, food for 4 hours, and refrain from exercise for 24 hours prior to this visit. Subjects will be asked to wear a short-sleeved shirt. If they do not bring one, we will provide one for them.

Endothelial Function: An 18 gauge catheter will be placed in an antecubital vein by a registered nurse or nurse practitioner. We will collect blood samples for the measurement of electrolytes, serum creatinine, estradiol, progesterone, testosterone, follicle stimulating hormone, angiotensin II, aldosterone, renin, norepinephrine, and endothelin-1 (90 mL). The blood samples will be stored in a freezer in the Physiology Core Lab until the time of analysis. After the samples are analyzed they will be destroyed at UD. The tubes will be labeled with subject numbers; no names will appear on the tubes. In addition we will collect some cells from the wall of the vein. Two sterile J-wires are inserted through the IV catheter and gently moved back and forth inside the vessel. One wire is used at a time. The wires are then transferred to a 50mL conical tube with endothelial dissociation buffer. The cells are rinsed and recovered by centrifugation. The cells are then fixed to coverslips, and stored in the freezer to be stained and analyzed for protein expression of ET-1 and ET-B receptors in batches at a later date. Large blood vessel function will then be assessed using two non-invasive techniques. First, a pressure probe is placed over the radial artery to record pressure waveforms. Then, the pressure probe will be placed over the carotid and femoral arteries to record pressure waveforms. A cloth tape will measure the distance between the carotid and femoral sites. Second, an ultrasound will be used to image the brachial artery. A small blood pressure cuff is placed just distal to the olecranon process. This cuff will be inflated for 5 minutes. Images of the brachial artery are collected continuously before, during, and for 3 minutes after cuff deflation. Changes in brachial artery diameter are used as an index of endothelial function.

Microdialysis placement: Four microdialysis fibers (Bioanalytical Systems) with a membrane length of 10mm and a 20-kDa cutoff will be inserted on the dorsal side of the forearm. Microdialysis fibers will be placed by [name] or doctoral student trained by [name]. Under sterile conditions the fibers are placed in the intradermal space with a 23-gauge needle used as a guide cannula. Ice is used on the site locally to numb the skin, reduce blood flow, and minimize release of vasoactive substances. The entrance and exit site on the skin are separated by at least 2 cm. The guide cannula is inserted horizontally in the dermis and the microdialysis fiber is fed through the guide cannula. The needle is removed, and the fiber left in place at a depth of \approx 2-5 mm. After placement, the fiber is perfused with lactated Ringers at a rate of 2 μ l/min using a syringe pump (Bioanalytical Systems, Inc.) for 90 minutes. This recovery period (after fiber insertion) is required to allow local skin blood flow (SkBF) to return to baseline before data measurements can be made. During the recovery period, the subject will be instrumented for the measurement of heart rate (ECG) and blood pressure.

ET-1 receptor antagonists: ET-A and ET-B receptor antagonists (BQ-123 and BQ-788, respectively, Sigma) will be perfused via intradermal microdialysis fibers while measuring skin blood flow (SkBF) at rest and during local heating. The antagonists will be dissolved in lactated Ringers solution and filtered using syringe microfilters (Whatman Puradisc 13 mm Syringe Filters, Florham Park, NJ). Following recovery from the microdialysis fiber placement, we will measure resting SkBF using laser Doppler flowmetry (LDF) for 15 min at all sites with the local heating devices off. Laser Doppler probes (MoorLAB, Temperature Monitor SH02, Moor Instruments, Devon, UK) which both measure and control local skin temperature, will be placed on the surface of the skin on the dorsal forearm over the microdialysis site. The laser Doppler probes will be maintained at 33°C during baseline and ET receptor antagonist infusion. Microdialysis fibers will then be perfused at 5.0 μ l/min for 45 minutes with the following drugs: the first fiber will be perfused with lactated Ringers; the second fiber will be perfused with 500 nM of the ET-A receptor antagonist (BQ-123)¹; the third fiber will be perfused with 300 nM of ET-B receptor antagonist (BQ-788)¹; the fourth fiber will be perfused with combined ET-A and ET-B receptor subtype antagonists (i.e. BQ-123 and BQ-788; 500 and 300 nM respectively). After perfusing the blocking agents, all four local heating devices will be raised until the skin temperature under the LDF probes reaches a stable temperature of 42°C². The SkBF response will be measured at each microdialysis site until a stable plateau is reached after heating. The microdialysis perfusions of antagonists will continue throughout the local heating response to maintain ET-A and ET-B receptor inhibition. Each series of perfusions will be followed by a perfusion of sodium nitroprusside (SNP, 28 mM) through the microdialysis fiber combined with local heating to 43°C to determine maximal SkBF. Cutaneous vascular conductance (CVC) will be calculated as mean SkBF/mean arterial pressure. We will collect blood samples for the measurement of estradiol, progesterone, testosterone, and endothelin-1 at the end of the recovery period just prior to beginning the perfusions, and again prior to maximal heating.

Perfusion of the ET-A and ET-B receptor antagonists, BQ-123 and BQ-788, either in arteries or skin vessels in humans, is an acceptable and safe experimental technique. Included is a list of the published research studies utilizing this technique:

- ¹Wenner MM et al. Endothelin B receptor contribution to peripheral microvascular function in women with polycystic ovary syndrome. JPHYS 2011.
- Kellogg DL et al. Gender differences in the endothelin-B receptor contribution to basal cutaneous vascular tone in humans. J Appl Phys 2001.
- Stauffer BL et al. Sex differences in endothelin-1-mediated vasoconstrictor tone in middle-aged and older adults. Am J Physiol Regul Integr Comp Physiol. 2010.

Losartan administration: At the completion of visit 3, women with high BP will be given 7 days of losartan (50mg), and be instructed to take the study medication once per day (at nighttime before bed). Losartan is a medication given to treat hypertension. Losartan administration will be overseen by [name].

Visit 3: Blood draw. This visit will occur one week after starting losartan. This visit will last \sim 20 minutes. Participants will report to the Physiology Core Laboratory at the STAR Health Sciences complex. Participants will be seated, and 10mL of blood will be drawn from a vein. Serum electrolytes and creatinine will be assessed to ensure using losartan in not having adverse effects on kidney function or electrolytes. If serum potassium is >5.2 mmol/L or creatinine is $>50\%$ over baseline values, the PI will contact the study physician [name], and he will determine if the medication will be discontinued and the participant be removed from the study. Elevated levels

typically resolve on their own upon cessation of drug therapy. Rarely, acute renal injury or cardiac arrhythmia's may develop. Additional medical follow-up may be instructed by [name], determined on a case-by-case basis (depending on individual responses to the medication), either to the emergency room or to the PCP. They will also be weighed. Women will be given another 7 days of losartan (50mg) and instructed to take the medication once per day (at nighttime before bed). Women will also be given a 24 hour ambulatory blood pressure monitor, and instruction on how to wear and operate the monitor. They will don the monitor the day before Visit 4. The blood pressure monitor measures BP every 20 minutes during the day, and every 30 minutes at night. Women will return the monitor the fourth visit.

Visit 4: Blood Vessel Assessment 2: The fifth visit is will occur 14 days after beginning losartan. This visit is approximately 5 hours long, and is identical to Visit 2 (Blood Vessel Assessment 1).

Visit 5: VO₂max Testing. This visit will last ~1 hour. Participants will be fasted from alcohol and caffeine for 12 hours, food for 4 hours, and exercise for 24 hours prior to testing. Exercise tests will be conducted in the stress testing laboratory in the NMPCC and overseen by a Certified Exercise Physiologist and Nurse Practitioner after clearance from the study physician, [name]. A resting 12-lead ECG and blood pressure will be taken in the supine and standing position. If resting BP is $\geq 200/110$ mmHg, the test will not be performed. A standard ramp treadmill protocol will be used, consisting of 1.5-minute stages where the speed and grade is increased incrementally. Expired gases will be collected and analyzed using the Parvo Medics Metabolic Cart. Exercise BP, HR, and ECG will be taken throughout, along with ratings of perceived exertion. This is a symptom-limited metabolic stress test; test termination criteria are based on ACSM guidelines (RER ≥ 1.10 , plateau in HR or VO₂ despite increased workload), and absolute indications for test termination such as chest pain, ECG abnormalities or arrhythmias, BP $>250/115$ mmHg, or participants request to stop. [name] will review the exercise test results. The NMPCC will send the test results to be read and interpreted by their cardiologist, [name]. In the event of a positive test or if additional follow up is needed, the NMPCC will contact the participant's primary care doctor.

Procedures in Normotensive Women (4 visits):

Visit 1: Screening/orientation: The first visit is about 1 hour long and includes

- 1). Completion of informed consent, medical history, and menstrual cycle history
- 2). Measures of height and weight,
- 3). Measures of resting blood pressure and 12-lead electrocardiogram
- 4). Blood Draw

Participants will be fasted from food, caffeine, and alcohol (12 hours) and exercise (24 hours). Informed consent will be obtained by [name], study PI, or doctoral student trained by [name]. Subjects will also be familiarized with the laboratory and experimental procedures. The blood draw and electrocardiogram will be done by a trained healthcare professional at the Nurse Managed Primary Care Center (NMPCC). Blood will be analyzed for cholesterol, c-reactive protein, electrolytes, kidney and liver function, and blood glucose (sugar). All screening results will be reviewed by a Nurse Practitioner at the NMPCC. In the event that the test results are abnormal, the NMPCC will refer the subject to their physician for follow-up and they will not be able to participate in the research study. Participants will be provided a HIPAA authorization form that includes permission for sharing of patient protected health information with the research team. Women will also be given a 24 hour ambulatory blood pressure monitor, and instruction on how to wear and operate the monitor. They will don the monitor at the completion of Visit 1. The blood pressure monitor measures BP every 20 minutes during the day, and every 30 minutes at night. Women will return the monitor the next day. When they return the monitor, we will ask that they be seated for 5-10 minutes, and we will take 3 resting blood pressure measures using an automated brachial blood pressure cuff. At the end of this visit we will give participants a standard blood pressure monitor to take home (Omron). This device is often used for adults to monitor blood pressure at home. The device takes 3 blood pressures and reports the average of these readings on the device. Women will be instructed to take seated resting blood pressures at home 3 times each week for 2 weeks. Blood pressures should be taken in the morning, at lunchtime, and again in the evening. Instructions will be provided along with a log to record the readings and time of day. Participants will return the BP monitor and log when they return to the lab prior to Visit 2.

Two to three days prior to Visit 2, women will be given a 24 hour ambulatory blood pressure monitor, and instruction on how to wear and operate the monitor. They will don the monitor the day before Visit 2. The blood pressure monitor measures BP every 20 minutes during the day, and every 30 minutes at night. Women will return the monitor the third visit.

Visit 2: Blood Vessel Assessment 1: The second visit lasts approximately 5 hours. Measurements will be conducted in the Cardiovascular Core Lab at STAR Health Sciences Complex. Subjects will be asked not to drink alcohol and caffeine for 12 hours, food for 4 hours, and refrain from exercise for 24 hours prior to this visit. Subjects will be asked to wear a short-sleeved shirt. If they do not bring one, we will provide one for them.

Endothelial Function: An 18 gauge catheter will be placed in an antecubital vein by a registered nurse or nurse practitioner. We will collect blood samples for the measurement of electrolytes, serum creatinine, estradiol, progesterone, testosterone, follicle stimulating hormone, angiotensin II, aldosterone, renin, norepinephrine, and endothelin-1 (90 mL). The blood samples will be stored in a freezer in the Physiology Core Lab until the time of analysis. After the samples are analyzed they will be destroyed at UD. The tubes will be labeled with subject numbers; no names will appear on the tubes. In addition we will collect some cells from the wall of the vein. Two sterile J-wires are inserted through the IV catheter and gently moved back and forth inside the vessel. One wire is used at a time. The wires are then transferred to a 50mL conical tube with endothelial dissociation buffer. The cells are rinsed and recovered by centrifugation. The cells are then fixed to coverslips, and stored in the freezer to be stained and analyzed for protein expression of ET-1 and ET-B receptors in batches at a later date. Large blood vessel function will then be assessed using two non-invasive techniques. First, a pressure probe is placed over the radial artery to record pressure waveforms. Then, the pressure probe will be placed over the carotid and femoral arteries to record pressure waveforms. A cloth tape will measure the distance between the carotid and femoral sites. Second, an ultrasound will be used to image the brachial artery. A small blood pressure cuff is placed just distal to the olecranon process. This cuff will be inflated for 5 minutes. Images of the brachial artery are collected continuously before, during, and for 3 minutes after cuff deflation. Changes in brachial artery diameter are used as an index of endothelial function.

Microdialysis placement: Four microdialysis fibers (Bioanalytical Systems) with a membrane length of 10mm and a 20-kDa cutoff will be inserted on the dorsal side of the forearm. Microdialysis fibers will be placed by [name], or doctoral student trained by [name]. Under sterile conditions the fibers are placed in the intradermal space with a 23-gauge needle used as a guide cannula. Ice is used on the site locally to numb the skin, reduce blood flow, and minimize release of vasoactive substances. The entrance and exit site on the skin are separated by at least 2 cm. The guide cannula is inserted horizontally in the dermis and the microdialysis fiber is fed through the guide cannula. The needle is removed, and the fiber left in place at a depth of \approx 2-5 mm. After placement, the fiber is perfused with lactated Ringers at a rate of 2 μ l/min using a syringe pump (Bioanalytical Systems, Inc.) for 90 minutes. This recovery period (after fiber insertion) is required to allow local skin blood flow (SkBF) to return to baseline before data measurements can be made. During the recovery period, the subject will be instrumented for the measurement of heart rate (ECG) and blood pressure.

ET-1 receptor antagonists: ET-A and ET-B receptor antagonists (BQ-123 and BQ-788, respectively, Sigma) will be perfused via intradermal microdialysis fibers while measuring skin blood flow (SkBF) at rest and during local heating. The antagonists will be dissolved in lactated Ringers solution and filtered using syringe microfilters (Whatman Puradisc 13 mm Syringe Filters, Florham Park, NJ). Following recovery from the microdialysis fiber placement, we will measure resting SkBF using laser Doppler flowmetry (LDF) for 15 min at all sites with the local heating devices off. Laser Doppler probes (MoorLAB, Temperature Monitor SH02, Moor Instruments, Devon, UK) which both measure and control local skin temperature, will be placed on the surface of the skin on the dorsal forearm over the microdialysis site. The laser Doppler probes will be maintained at 33°C during baseline and ET receptor antagonist infusion. Microdialysis fibers will then be perfused at 5.0 μ l/min for 45 minutes with the following drugs: the first fiber will be perfused with lactated Ringers; the second fiber will be perfused with 500 nM of the ET-A receptor antagonist (BQ-123)¹; the third fiber will be perfused with 300 nM of ET-B receptor antagonist (BQ-788)¹; the fourth fiber will be perfused with combined ET-A and ET-B receptor subtype antagonists (i.e. BQ-123 and BQ-788; 500 and 300 nM respectively). After perfusing the blocking agents, all four local heating devices will be raised until the skin temperature under the LDF probes reaches a stable temperature of 42°C². The SkBF response will be measured at each microdialysis site until a stable plateau is reached after heating. The

microdialysis perfusions of antagonists will continue throughout the local heating response to maintain ET-A and ET-B receptor inhibition. Each series of perfusions will be followed by a perfusion of sodium nitroprusside (SNP, 28 mM) through the microdialysis fiber combined with local heating to 43°C to determine maximal SkBF. Cutaneous vascular conductance (CVC) will be calculated as mean SkBF/mean arterial pressure. We will collect blood samples for the measurement of estradiol, progesterone, testosterone, and endothelin-1 at the end of the recovery period just prior to beginning the perfusions, and again prior to maximal heating.

Perfusion of the ET-A and ET-B receptor antagonists, BQ-123 and BQ-788, either in arteries or skin vessels in humans, is an acceptable and safe experimental technique. Included is a list of the published research studies utilizing this technique:

- ¹Wenner MM et al. Endothelin B receptor contribution to peripheral microvascular function in women with polycystic ovary syndrome. JPHYS 2011.
- Kellogg DL et al. Gender differences in the endothelin-B receptor contribution to basal cutaneous vascular tone in humans. J Appl Phys 2001.
- Stauffer BL et al. Sex differences in endothelin-1-mediated vasoconstrictor tone in middle-aged and older adults. Am J Physiol Regul Integr Comp Physiol. 2010.

At the completion of Visit 2, women will be given a 24 hour ambulatory blood pressure monitor, and instruction on how to wear and operate the monitor. They will don the monitor the day before Visit 3. The blood pressure monitor measures BP every 20 minutes during the day, and every 30 minutes at night. Women will return the monitor the third visit.

Visit 3: Blood Vessel Assessment 2: The fourth visit is will occur 14 days after Visit 2. This visit is approximately 5 hours long, and is identical to Visit 2 (Blood Vessel Assessment 1).

Visit 4: VO₂max Testing. This visit will last ~1 hour. Participants will be fasted from alcohol and caffeine for 12 hours, food for 4 hours, and exercise for 24 hours prior to testing. Exercise tests will be conducted in the stress testing laboratory in the NMPCC and overseen by a Certified Exercise Physiologist and Nurse Practitioner. A resting 12-lead ECG and blood pressure will be taken in the supine and standing position. If resting BP is $\geq 200/110$ mmHg, the test will not be performed. A standard ramp treadmill protocol will be used, consisting of 1.5-minute stages where the speed and grade is increased incrementally. Expired gases will be collected and analyzed using the Parvo Medics Metabolic Cart. Exercise BP, HR, and ECG will be taken throughout, along with ratings of perceived exertion. This is a symptom-limited metabolic stress test; test termination criteria are based on ACSM guidelines (RER ≥ 1.10 , plateau in HR or VO₂ despite increased workload), and absolute indications for test termination such as chest pain, ECG abnormalities or arrhythmias, BP $>250/115$ mmHg, or participants request to stop. The NMPCC will send the test results to be read and interpreted by their cardiologist, [name]. In the event of a positive test or if additional follow up is needed, the NMPCC will contact the participant's primary care doctor.

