How will data be analyzed and reported?

Cutaneous vascular conductance (CVC) will be calculated as mean SkBF/mean arterial pressure. While the results of this research will be published, neither participant name nor identity will be revealed.

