Sample size estimates were calculated for our main outcome variables in Specific Aim 1 based on previously published data in normotensive and pre-hypertensive adults utilizing arterial infusions of the ET-1 receptor antagonist. A three level 2x2 General Linear Mixed Model will be used to compare normotensive and hypertensive PMW on the outcomes. The hierarchical structure is needed as sites are nested within measurements, which are nested within individuals. The model assumptions of linearity and normality, will be evaluated using Box-Cox and Shapiro-Wilk tests, respectively. Outliers and influential cases will be screened for and removed. The covariance structure will be chosen using nested model comparisons. Violations of the assumptions will be remedied using transformations suggested by the Box-Cox test. *Post-hoc* comparisons will have the Bonferroni adjustment applied. The alpha is set at 0.05 for each analysis, and will be adjusted by the number of primary dependent variables to control for multiple comparisons. In order to find a large effect ($\rho\eta^2 = 0.50$), a sample of size of 38 women is required to achieve a power greater than 0.8. In order to account for screen failures, subject attrition and potential microdialysis fiber failure, we will recruit 60 women (30 normotensive and 30 hypertensive).

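### Pre-drug resting flow is recorded at every skin site but given no stated analytic role; as a site-level covariate it could sharpen the antagonist-versus-Ringer contrasts at almost no cost

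*Combined protocol and SAP*

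**What the plan says.** Section 6 (Procedures), under ET-1 receptor antagonists, gives the same sequence for women with high blood pressure and for normotensive women. After recovery from fiber placement, "we will measure resting SkBF using laser Doppler flowmetry (LDF) for 15 min at all sites". The second assessment is described as identical, so each woman yields 4 sites × 2 visits = 8 pre-drug site records.

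The perfusions follow, one fiber per condition: "the first fiber will be perfused with lactated Ringers", and the other three receive the ET-A antagonist, the ET-B antagonist and their combination. After the heating response, each series ends with nitroprusside "combined with local heating to 43°C to determine maximal SkBF".

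Section 10 (Data) gives the only outcome formula: "Cutaneous vascular conductance (CVC) will be calculated as mean SkBF/mean arterial pressure". The Statistical Plan, first paragraph, adds: "A three level 2x2 General Linear Mixed Model will be used to compare normotensive and hypertensive PMW on the outcomes", with the reason that "sites are nested within measurements, which are nested within individuals". It does not name the two factors, or the phase (rest, on-drug rest or heating plateau) that supplies the outcome. The second paragraph lists candidate covariates: age, body composition, aerobic capacity and time since menopause. Each enters only if the groups differ significantly on it.

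On the thermal conditions of the resting record, section 6 says both "with the local heating devices off" and "The laser Doppler probes will be maintained at 33°C during baseline and ET receptor antagonist infusion".

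**The concern.** An antagonist effect here is a comparison between different patches of skin on one forearm. Patches can differ in flow before any drug reaches them, and the resting record is where such differences would show. If the analysis ignores that record, they count as error in the contrast.

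The site level of the model does not solve this. With one fiber per condition per visit, and one value per site for a given phase, site variance cannot be separated from residual variance. Dividing by arterial pressure does not help either, because pressure is common to all four sites. Nor can the covariate rule bring the record in, since it works by comparing person-level variables between groups.

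At stake is precision in the contrasts that isolate each receptor, and in how those contrasts differ between groups and before and after losartan, in a study planned on 38 women.

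**Working it through.** **Inputs from the documents.** Four sites, two visits, one fiber per condition per visit (section 6); outcome CVC = SkBF/MAP (section 10); planned sample of 38 women at partial eta-squared 0.50 (Statistical Plan, first paragraph).

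**Input not in the documents.** r, the correlation between pre-drug and on-drug deviations of a site from the woman's own mean at that visit. It is assumed below over a range.

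**The plan's own figure.** Partial eta-squared 0.50 gives f² = 0.50/(1 − 0.50) = 1. With a noncentral F, a two-group test at alpha 0.05 needs 12 women (power 0.876), and power at 38 is about 1.00. So 38 exceeds power 0.8 but does not reproduce as the number required. The calculation gives no site standard deviation and no baseline correlation, so the present point cannot be checked through the sample size.

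**Effect of using the resting record.** The variance of an antagonist-minus-Ringer contrast, relative to using the on-drug value alone, is:
- covariance adjustment: 1 − r²
- change from baseline: 2(1 − r)

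| assumed r | adjusted variance | reduction | SE factor √(1 − r²) | change-score variance |
|---|---|---|---|---|
| 0.2 | 0.96 | 4% | 0.980 | 1.60 |
| 0.3 | 0.91 | 9% | 0.954 | 1.40 |
| 0.5 | 0.75 | 25% | 0.866 | 1.00 |
| 0.7 | 0.51 | 49% | 0.714 | 0.60 |

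The change score loses precision whenever 2(1 − r) > 1, that is, r < 0.5. Covariance adjustment does not, apart from the cost of estimating one slope.

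**Check by simulation.** With 38 women, two groups, two visits, four sites and the covariate centred within woman and visit, the variance ratios at r = 0.3, 0.5 and 0.7 were 0.90, 0.78 and 0.52 for the simple contrast. They were 0.90, 0.75 and 0.50 for its group-by-visit difference. These agree with 1 − r² to within simulation error. At r = 0 the loss was under 1%.

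**What the adjustment cannot reach.** The centred covariate sums to zero over a woman's usable sites at a visit. It therefore leaves each woman-visit mean unchanged, and with it any group, visit or group-by-visit effect averaged over sites.

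**The site maximum as an alternative.** Suppose site differences are purely multiplicative with coefficient of variation s, and each flow measurement has an assumed coefficient of variation e = 0.15. On the log scale, dividing by the site's maximum changes the contrast variance by the factor 2e²/(s² + e²):
- s = 0.10: 0.045/0.0325 = 1.38
- s = 0.20: 0.045/0.0625 = 0.72
- s = 0.30: 0.045/0.1125 = 0.40
- s = 0.40: 0.045/0.1825 = 0.25

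Such scaling can remove much of the site variation, or can add noise when sites differ little. It does not touch differences that are not multiplicative.

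**The case against.** The strongest reply is that the plan is silent and does not exclude the record. Section 6 treats flow at rest as a measurement of interest, and the 2x2 factors and the measurement level are undefined, so resting conductance could be an outcome or a repeated phase. This stands. A reader might infer that the resting data are discarded; the documents support only that no use is specified.

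Second, each site also has a maximal-flow measurement. If conductance is expressed relative to it, multiplicative site differences are already gone and the gain from the resting record is not the 1 − r² tabulated for absolute conductance. This stands as a condition: the plan does not state that scaling.

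Third, if the 2x2 is group by visit, averaged over sites, the covariate gives no gain there. Correct; the benefit is confined to antagonist contrasts and their interactions, which the plan does not write out.

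Fourth, r is unanchored, and resting flow may predict the 42°C plateau less well than it predicts on-drug rest. Correct. The table is a range, not an estimate.

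Fifth, this is efficiency, not validity. A reader might infer bias from fiber position, but the documents give no rule tying drug to position, so none is shown. A reader might also infer that the study is underpowered; at the plan's own effect size, power at 38 is about 1.00, so that is not shown either.

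None of this supplies a reason to leave an available site-level baseline without a stated role.

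**Conclusion.** The point holds as a low-cost gain in precision. The plan collects a pre-drug value at every site at both visits and states no analytic role for it. Pre-existing patch differences therefore enter the error of the antagonist-versus-Ringer contrasts and their differences by group and visit, unless conductance is scaled to the site maximum. That scaling is unstated and would remove only multiplicative differences.

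The size is conditional. Contrast variance falls by between 4% and 49% as r runs from 0.2 to 0.7, and possibly by less for the heating plateau. The result assumes one slope common to drug conditions, groups and visits, and a resting record thermally comparable with the drug period. The second assumption cannot be taken for granted while section 6 describes heater state in two ways.

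The documents do not support reading this as a bias, as a threat to the planned power, or as a gain for group or losartan effects averaged over sites.

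**What to change.** 1. Reconcile the two statements in section 6, in both groups' procedures, on heater state during the resting record.
2. State the outcome scale (absolute conductance or share of the site's maximum), the phase analysed and the two model factors.
3. In the mixed model for antagonist contrasts, add each site's pre-drug resting conductance as a covariate, on the same scale as the outcome. Centre it on the mean of that woman's usable sites at that visit. A usable site has both a resting and an outcome value, so the rule still works after the fiber failure that the Statistical Plan anticipates. Centring also keeps the covariate from absorbing group effects or the losartan effect on resting flow at the second assessment.
4. Use covariance adjustment and not a change score, which loses precision if r is below 0.5.
5. Say that the adjustment serves site contrasts and their interactions with group and visit, and report the estimated slope separately for on-drug rest and the heating plateau.

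Cost: one degree of freedom per outcome model under a common slope, a few sentences in the Statistical Plan, and no new measurement. If r is near zero, the loss is under 1% of variance.
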